In the Emergency Department (ED), patients frequently seek medical treatment for vaginal complaints consistent with a possible sexually transmitted infection (STI). It is known that for our inner city population in Baltimore, Maryland, providers have a low threshold to initiate treatment for *Neisseria gonorrhoeae* and *Chlamydia trachomatis* in the ED prior to knowing the results of diagnostic tests. This is due to the delaying in receiving the results and the possible consequences of leaving an infected patient untreated. Specifically, it has been shown that untreated infections leave patients at increased risk for development of pelvic inflammatory disease, tubo-ovarian abscess, cancer, infertility, pregnancy complications (including ectopic pregnancy) and increased shedding of the human immunodeficiency virus amongst other morbidities (CDC, 2014). Currently, testing at our facility for gonorrhea and chlamydia involves sending urine or cervical specimens to an off-site laboratory for polymerase chain reaction (PCR) evaluation. Results of this testing are not available for up to 2 to 3 days after the specimen is obtained. Empiric treatment is often given in the ED because of this delay in obtaining results and the difficulties surrounding patient follow up from the ED. Some patients are not offered treatment despite having symptoms suggestive of a sexually transmitted infection. Overtreatment brings up concerns relating to antibiotic resistance, increased healthcare costs and potential for adverse reactions to the antibiotics (Newman et al., 2007). Undertreatment of patients increases their risk of developing complications related to the infection. The use of a rapid-turnaround test (RTAT) could potentially provide results in as little as 90 minutes while the patient waits in the ED. The same factors hold true for the care of patients in the recently opened Urgent Care Center at UMMC. The Urgent Care Center is staffed by faculty physicians and nurse practitioners from the Department of Emergency Medicine and many, but not all, patients with complaints consistent with STI are now managed in the Urgent Care Center. This study aims to determine if use of a RTAT improves the appropriate treatment of patients with signs and symptoms suggestive of a STI. Additionally, the effect that this testing would have on healthcare costs and its impact on patient length of stay will be analyzed.

Research Plan

A. Specific Aims

The study aims to assess whether an FDA-approved rapid turnaround test (RTAT) for *Neisseria gonorrhoeae* and *Chlamydia trachomatis* infections will lead to more appropriate antibiotic prescription in the emergency department.

Secondary outcomes include the RTAT's effect on length of emergency department stay, result congruence with the PCR method regardless of specimen source, result congruence with PCR method differentiating between urine and cervical specimens, estimation of the effect of utilization of the RTAT will have on healthcare costs, its impact on satisfaction, and on further healthcare utilization.

Null hypothesis: Point of care use of the GC/CT RTAT in female ED patients for whom there is a suspicion of either disease results in no more appropriate antibiotic prescription than in patients who receive empiric therapy before GC/CT PCR results return.

B. Background Significance

Infections with *Chlamydia trachomatis* and *Neisseria gonorrhoeae* are the most commonly reported sexually transmitted diseases in the United States. In 2014, there were 1,441,789 cases of chlamydia and 350,062 cases of gonorrhea reported in the US (CDC, 2014). Baltimore ranks 4th in US metropolitan areas for rates of chlamydia at 1245 cases per 100,000 and 17th for rates of gonorrhea at 314 cases per 100,000 (CDC, 2014).

Untreated infections leave patients at increased risk of pelvic inflammatory disease, infertility, ectopic pregnancy and shedding of the human immunodeficiency virus among other morbidities (Johnson and Mak, 2002). Because of this, providers have a low threshold to initiate treatment for gonorrhea and chlamydia. In a previous retrospective analysis done at this hospital and a nearby community hospital it was found that patients were inappropriately treated 21% of the time (Holley et al., 2015). Inappropriate treatment is defined for the purpose of this study as administration of antibiotics to treat GC/CT in the absence of GC/CT infection or failure to give antibiotics in the presence of GC/CT infection. For the purposes of the study the "gold standard" result will be that of the PCR test and not the RTAT. By evaluating the impact of a rapid turnaround test for GC/CT, we will determine if there is a reduction in the rate of inappropriate treatment. Furthermore, we will analyze the economic, temporal, and qualitative impacts of altering the current paradigm.

C. Research Design

A prospective, nonblinded, randomized controlled trial will be conducted at the Adult Emergency Department at the University of Maryland Medical Center and Adult Urgent Care Center, which is managed by the Department of Emergency Medicine, located in Baltimore, Maryland.

Sample size calculation was performed assuming that the control group will be given the wrong treatment 21% of the time. It is assumed that the use of the rapid TAT will reduce this by about 95%. The following variables were used to calculate the sample size: alpha = 0.05 power = 0.8 P0 = 0.21 P1 = 0 M = 1. It was determined that 43 patients are required in each group.

Assuming a dropout rate of up to 10% this study will enroll 48 patients into each of the study groups.

Patients who consent to participation will be randomly selected into either the control group or the experimental group.

- i. Control group - GC/CT testing done only via standard PCR test
- ii. Experimental group - GC/CT testing done using both rapid TAT and standard PCR tests

Subjects will be randomly assigned to either the study or control groups. Randomization will be performed at the level of the patient, with the study team member using blind-sequenced subject folders. Patients will be assigned a sequential subject number with a corresponding folder for the study team member. This folder will contain the randomly assigned treatment allocation and data collection forms. Randomization for the subject folders will be performed using an online randomization tool.

Study team members will assess patients for inclusion and exclusion criteria. Patients who meet criteria will be invited to participate in the study.

Informed Consent Process: Patients who meet study criteria and desire to be a part of this study, will be consented prior to procedure. A copy of the consent and research proposal will be provided and reviewed with the patient. This study will be voluntary and confidential. All patient identification information will be kept in the principal investigator's locked office.

Study Location: Study will be conducted in the Adult Urgent Care Center and Emergency Department at the University of Maryland Medical Center.

All study participants that will be enrolled will undergo standard of care testing to evaluate for a sexually transmitted infection. If the result of the RTAT in the experimental group is "invalid" treatment will still be at the discretion of the provider using the information available including history, physical and determination of risk. No repeat testing with the RTAT is allowable as part of study procedures.

During the subject screening and consent process, we hope to identify subjects that are not willing to wait for the results of their testing should they be a part of the experimental group and not enroll them in the study. Should these subjects enroll in the study and subsequently change their mind about waiting for their results, they may choose to withdraw from the study and leave. If the RTAT sample is already being run on the machine at the time of the subject's departure, the subject will be contacted with the test result. If the test result is positive they will be counseled about appropriate next steps taking into account whether or not they received empiric treatment. All study participants that will be enrolled will undergo standard of care testing to evaluate for a STI. Per usual care at the University of Maryland Medical System, the clinical provider determines treatment at the time of initial evaluation using all the available clinical information. For patients assigned to the intervention group- If the subject leaves prior to completion of the RTAT then the clinical provider still determines treatment based on the information available.

In a study published by Gaydos et al in 2013, the Cepheid RTAT for chlamydia in females demonstrated sensitivities for endocervical, vaginal, and urine samples of 97.4%, 98.7%, and 97.6%, respectively, whereas, for gonorrhea in females the sensitivities for endocervical, vaginal, and urine samples were 100.0%, 100.0%, and 95.6%, respectively. [doi: 10.1128/JCM.03461-12]. This demonstrates a very high accuracy for the test under consideration in the current study. There is always the possibility of incongruent results between

the standard of care PCR test and the Cepheid RTAT. If this happens the study subject will be contacted and arrangements will be made to have the appropriate care provided.

The possible outcomes for test results are:

1. RTAT is negative and PCR is negative: no adjustment needs to be made to care of the subject.
2. RTAT is negative and the PCR is positive: if the patient was not treated empirically during the index visit, as usual care for the department, the patient will be contacted and arrangements made to provide appropriate care. This contact is made as part of the quality assurance program of the department. The study team will verify this contact was completed.
3. RTAT is positive and PCR is positive: no adjustment needed if the clinician treated the patient during the index visit. If the patient was not treated then the same process will occur as in scenario 2.
4. RTAT is positive and PCR is negative: if the subject was not treated during the index visit then they will be contacted by the study team to explain that two highly accurate tests gave different results. The patient will be offered the opportunity to return for treatment. If the subject was treated during the index visit then they will be contacted by the study team to explain that two highly accurate tests gave different results. As treatment was already given there would be no change to the management of the patient.

D. Subjects and Sampling

a. Inclusion Criteria

- Female patients age 18-55
- Signs or symptoms consistent with sexually transmitted infection
- Medical provider willing to consider the result of the rapid turnaround test in the decision to treat for gonorrhea/chlamydia
- Must have a urine specimen obtained and a pelvic exam performed as part of the anticipated standard of care evaluation
- Patient agrees to wait for results of RTAT testing, in the likelihood they are assigned that group.
- Provides informed consent

b. Exclusion Criteria

- Age < 18 or > 55
- Signs of systemic infection
- Patient in whom the provider is unwilling to consider the result of the rapid turnaround test
- Patient who reports being treated for either gonorrhea or chlamydia in the preceding 3 months
- Patients undergoing evaluation for sexual assault
- Patients that are known to be pregnant or express concern that they may be pregnant
- Incarcerated patients
- Students/Employees of the facility
- Presence of any other condition(s) that the investigator feels makes the patient unsuitable for study inclusion.

c. Informed Consent Process: Patients who meet study criteria will be consented prior to participation in any study related procedure. A copy of the consent form and privacy form

(HIPAA) will be provided and reviewed with the patient. This study will be voluntary and confidential. All study data with potential patient identifiable information will be kept in a locked office.

- d. Study Location: Study will be conducted in the Adult Urgent Care Center at the University of Maryland Medical Center, which is managed by the Department of Emergency Medicine and in the Adult Emergency Department.
- e. Potential Problems: Insufficient number of patients who meet all inclusion and exclusion criteria. Lack of eligible patients willing to participate in the study.

E. Data Collection and Objectives

Primary Outcomes:

- To evaluate the effect of utilizing a rapid turnaround GC/CT test on treatment of patients with possible STIs

Secondary Outcomes:

- To evaluate the effect of utilizing a rapid turnaround GC/CT test on length of stay in the Emergency Department
- To compare the congruence of test results between the rapid turnaround GC/CT test with the usual care test (send out PCR) in those subjects that have both performed (Experimental Group).
- To evaluate the effect of utilizing a rapid PCR test on healthcare costs.
- To evaluate patient satisfaction with the 2 diagnostic groups.
- To compare need for additional healthcare utilization between the groups.

F. Methods

Patients meeting eligibility criteria and who have signed the research informed consent will be enrolled in this study. The subject will be randomly assigned to either the control or the experimental group. We will utilize the online pre-randomization website:

<https://www.graphpad.com/quickcalcs/randomize1.cfm> for randomization into one of the two groups. All subjects will be assigned a study participant number. Subject data collected will include demographic information, symptoms of the present illness and physical exam findings.

The control group will be followed according to standard of care as listed below in Question 2. The medical records will be reviewed following treatment and discharge to determine if this subject received empiric treatment.

The experimental group will be followed according to standard of care with the following additional research analysis: A cervical swab sample will be analyzed with the RTAT. The RTAT has been approved by the FDA for diagnosing suspected sexually transmitted infections (STIs).

For the experimental group, a study team member will verbally obtain the consent of the treating provider for the subject as to whether or not they would empirically treat the study subject if the RTAT was not being run. After results of the RTAT test are obtained the treating provider will be given the results. The treating provider can determine the course of treatment based on this test and their history of clinical exam findings. Subjects with negative RTAT results are not precluded from receiving treatment. If the result of the RTAT of the experimental group is

“invalid”, the subject will be treated according to usual care and, at the discretion of the provider. This may be to either empirically treat or wait to treat pending the results of the usual care tests. This process to either treat or withhold antibiotics for a suspected sexually transmitted infection (STI) until the culture results have returned is in accordance with the standard of care for the University of Maryland Medical System.

For both groups- 1) Additional data will be collected on length of stay in the Adult Emergency Department and Urgent Care Center. The time of interest is from when the subject first undergoes pelvic examination to the time that the subject leaves the treatment area.

2) A patient satisfaction survey to compare assigned treatment groups. 3) Telephone contact 1 to 2 weeks after enrollment. Using a standardized interview form they will be asked about resolution of symptoms, need for additional treatment, compliance with treatment, and satisfaction.

Subjects who have enrolled in the study and subsequently changed their mind about waiting for their results may choose to leave. All study participants who will be enrolled will undergo standard of care testing to evaluate for a STI. Per standard of care at the University of Maryland Medical System, they will be treated empirically or have antibiotics withheld at the discretion of the provider until the culture results have returned, after the subject has been discharged.

Regardless of the group assignment, any standard of care nucleic acid amplification tests that are positive; and the subject did not receive adequate antibiotics will be contacted (as per standard of care). These study subjects will be managed as part of usual care by the quality assurance (QA) program. These subjects may be asked to return to the emergency department for further evaluation, at the discretion of the study subject and QA resident, again as per standard of care.

The GeneXpert IV Device manufactured by Cepheid will be located in the Adult Emergency Department point-of-care (POC) laboratory area. Once we have CICERO approval, we will obtain a laboratory and POC approval to maintain the donated device in this area. RTAT performance will be done by members of the research team, trained using the materials made available by the manufacturer.

Section 2: Procedures Already Being Performed for Diagnostic or Treatment Purposes

Females presenting to the Adult Emergency Department or Urgent Care Center will undergo the standard evaluation appropriate for suspected chlamydial or gonococcal infections. As part of usual care, vitals signs will be measured, a physical exam will be performed and a urine specimen will be obtained for a urinalysis and a pregnancy test. A pelvic exam will be performed to collect endocervical samples for nucleic acid amplification analysis. This cervical swab is done for the purpose of diagnosis. The results of the cervical swab may take up to 2 days. This process to either treat or withhold antibiotics for a suspected sexually transmitted infection (STI) until the culture results have returned is in accordance with the standard of care for the University of Maryland Medical System. As shown previously, these patients are often started on empiric therapy that is not necessary based on the final results of testing.

Review of Literature:

In 2007, Newman et al. [doi: 10.1086/511422], gave an update discussing the management of Gonorrhea in the United States. It was discussed that *Neisseria gonorrhoeae* has the ability to develop antibiotic resistance. This paper discusses criteria for treating gonorrhea and how to treat gonorrhea at varying levels of antimicrobial resistance. Newman also discusses treatment options for patients that have adverse reactions to cephalosporins or quinolones.

In 2013, Tabrizi et al. [doi: 10.1128/JCM.00806-13], evaluated the sensitivity and specificity of the GeneXpert CT/NG in its ability to detect *Chlamydia trachomatis* and *Neisseria gonorrhoeae* compared to closely related bacterial species. In all isolates tested of both *N. gonorrhoeae*, the Xpert detected all isolates, and reported no false positives when testing other *Neisseria* species. Results were similar for *C. trachomatis*, Xpert correctly detected all 15 different serovars. This paper concludes that the GeneXpert CT/NG assay is highly sensitive and highly specific.

In 2013, Gaydos et. al. [doi: 10.1128/JCM.03461-12] completed a review of the Cepheid GeneXpert and its potential use in clinical settings. This review discussed how the short time interval required for the assay (90 minutes) might allow patients to be treated for CT/NG before leaving the clinic. This could in turn reduce the number of untreated patients who later may develop pelvic inflammatory disease. The review mentions how possible barriers to this could include patients refusing to wait the 90 minutes required for the assay. There may also be financial barriers to implementing this form of testing.

In 2014, the Center for Disease Control published its annual STD surveillance report. In this report, it was shown that infections with *Chlamydia trachomatis* and *Neisseria gonorrhoeae* are the most commonly reported sexually transmitted diseases in the United States, with 1,441,789 cases of chlamydia and 350,062 cases of gonorrhea in the US in 2014.

In 2014, Gaydos C. A [doi: 10.1586/14737159.2014.871495], reviewed the use of a new rapid real-time PCR, the Cepheid GeneXpert® (Xpert) CT/NG assay, for *Chlamydia trachomatis* and *Neisseria gonorrhoeae*. They found that the rapid, real time PCR nucleic acid amplification test demonstrated near-perfect sensitivity and specificity in urogenital specimens. Results are provided in approximately 90 minutes, and the Xpert has a platform for testing specimens directly from patients, with no hands-on manipulation from specimen loading to receiving results. This paper highlights the potential of the Xpert technology to change the diagnostic protocol in the clinical setting.

In 2015, Brook [doi:10.1136/setrans-2014-051997] completed a study that evaluated the utility of point-of-care and rapid nucleic acid amplification techniques for the diagnosis of chlamydia and gonorrhea. It was found in the literature review that GeneXpert was better than other point-of-care tests with a sensitivity of 97.5%–98.7% and a specificity of 99.4%–99.9%. It also found that GeneXpert was the best for gonorrhea as well with a sensitivity of 96–100% and specificity of 99.9–100%. It was determined that using rapid NAAT alone could allow for a reduction in average time until treatment but only a small reduction in sensitivity/specificity.

In 2015, Holley et al. [doi: 10.1016/j.ajem.2015.06.009], examined the rates of overtreatment of CT and NG infections in the ED. This study found that the rate of overtreatment in the 2 inner-city EDs studied was 86%. Currently, there is no protocol that guides ED providers on when to treat patients in whom NG or CT infection is being considered, and presently providers will tend to treat patients empirically for both STDs without any objective data. This study cited the need for reexamination of the current protocol in evaluating possible CT/NG infection.

Reference List:

1. Brook, G. The performance of non-NAAT point-of-care (POC) tests and rapid NAAT tests for chlamydia and gonorrhoea infections. An assessment of currently available assays. *Sex Transm Infect sextrans–2014–051997* (2015). doi:10.1136/sextrans-2014-051997
2. Centers for Disease Control and Prevention. Sexually transmitted disease surveillance. 2014. Atlanta: US Department of Health and Human Services; 2014.
3. Gaydos, C. A. Review of use of a new rapid real-time PCR, the Cepheid GeneXpert® (Xpert) CT/NG assay, for Chlamydia trachomatis and Neisseria gonorrhoeae: results for patients while in a clinical setting. *Expert Review of Molecular Diagnostics* 14, 135–137 (2014). doi: 10.1586/14737159.2014.871495.
4. Gaydos, C. A. et al. Performance of the Cepheid CT/NG Xpert Rapid PCR Test for Detection of Chlamydia trachomatis and Neisseria gonorrhoeae. *J. Clin. Microbiol.* 51, 1666–1672 (2013). doi: 10.1128/JCM.03461-12.
5. Holley, C. E., Van Pham, T., Mezzadra, H. M., Willis, G. C. & Witting, M. D. Overtreatment of gonorrhea and chlamydial infections in 2 inner-city emergency departments. *The American Journal of Emergency Medicine* 33, 1265–1268 (2015). doi: 10.1016/j.ajem.2015.06.009.

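### The null hypothesis takes empirically treated patients as its comparator, whereas the trial randomises to a PCR-only control group that includes untreated patients

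*Protocol*

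**What the plan says.** The null hypothesis in A. Specific Aims states that RTAT use in female ED patients with suspected infection "results in no more appropriate antibiotic prescription than in patients who receive empiric therapy before GC/CT PCR results return".

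C. Research Design defines the arms by the test used: "Control group - GC/CT testing done only via standard PCR test", against both tests in the experimental group. It leaves treatment open: under usual care "the clinical provider determines treatment at the time of initial evaluation using all the available clinical information". F. Methods and Section 2 both describe usual care as a choice: "This process to either treat or withhold antibiotics for a suspected sexually transmitted infection (STI) until the culture results have returned" is said to be the standard of care. For controls, F. Methods adds: "The medical records will be reviewed following treatment and discharge to determine if this subject received empiric treatment". The introduction acknowledges that "Some patients are not offered treatment despite having symptoms suggestive of a sexually transmitted infection".

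B. Background Significance defines inappropriate treatment, with PCR as reference, as antibiotics given without infection or "failure to give antibiotics in the presence of GC/CT infection". It describes the aim without reference to treatment received: "we will determine if there is a reduction in the rate of inappropriate treatment".

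**The concern.** The comparator in the null and the randomised control group are different sets of patients. The first is formed by what the provider decided after randomisation. The second is formed by allocation and contains treated and untreated patients.

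Two things would follow from applying the null as worded. First, an RTAT arm kept whole would be compared with a selected part of the control arm, and randomisation would no longer protect that comparison. Second, a control patient given no antibiotics could not enter the comparator. Undertreatment, one of the two errors in the endpoint, would largely disappear from the control side while still being counted in the RTAT arm. A hypothesis that sets out the trial's main question should describe the comparison that the trial randomises.

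**Working it through.** **1. The two comparators side by side.**

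- Null hypothesis (A. Specific Aims): patients given empiric therapy before the PCR result. Membership depends on treatment received.
- Control group (C. Research Design): patients tested by PCR only. Membership depends on allocation.
- Are they the same set? Only if every control is treated empirically. The introduction, C. Research Design, F. Methods and Section 2 all say or imply otherwise, and F. Methods establishes treatment from the records afterwards.
- Which set fits the endpoint? The full control group, because untreated infection is an error by definition.
- Which set fits the sample size? The full control group, because the 21% error rate is applied to the control group as a whole.

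**2. The sample size does not depend on the wording.** Inputs from C. Research Design: alpha 0.05, power 0.8, P0 = 0.21, P1 = 0, 1:1. Sidedness is not stated; two-sided is assumed here. The mean proportion is 0.105.

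- Uncorrected: n = [1.960·√(2·0.105·0.895) + 0.842·√(0.21·0.79)]² / 0.21² = 32.2.
- With continuity correction: (32.2/4)·[1 + √(1 + 4/(32.2·0.21))]² = 41.2, so 42 against the stated 43.
- Dropout: 43/0.9 = 47.8, so 48, as stated.
- Exact power of a two-sided Fisher test at 43 per group is 91.3% for 0.21 against 0, and 82.4% for 0.21 against 0.0105 (the 95% reduction given in words: 0.21·0.05).

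P0 already refers to the whole control group, so naming that group in the null changes none of this.

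**3. What the literal comparator could do (illustration only).** Suppose RTAT has no effect and 21% are wrongly treated in both arms. Let t be the share of controls treated and o the share of all controls overtreated, so that 0.21 − o are undertreated. If every infected patient who is treated is treated adequately, the error rate among treated controls is o/t. The values of t and o are assumptions. With 43 controls, t = 0.5 leaves 22 and t = 0.7 leaves 30. Each row compares them with 43 RTAT patients at 21%, two-sided Fisher, alpha 0.05.

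| t | o | o/t | Rejects, total | Favouring RTAT | Favouring control |
|---|---|---|---|---|---|
| 0.5 | 0.21 | 42% | 39.8% | 39.8% | <0.1% |
| 0.5 | 0.15 | 30% | 11.0% | 10.8% | 0.2% |
| 0.5 | 0.105 | 21% | 3.5% | 1.9% | 1.6% |
| 0.7 | 0.21 | 30% | 11.3% | 11.2% | 0.2% |
| 0.7 | 0.15 | 21.4% | 3.6% | 2.0% | 1.6% |
| 0.7 | 0.105 | 15% | 7.1% | 0.3% | 6.8% |

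The full randomised comparison (43 against 43, both 21%) rejects in 2.6%, split evenly. Three of the six scenarios falsely favour RTAT in more than 5% of trials, one falsely favours control, and two show little distortion. So even the direction of bias is not determined by anything in the protocol.

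**The case against.** The strongest reply is that this is loose wording which the rest of the protocol already resolves. The arms are defined by test. P0 is applied to the control group. The endpoint includes untreated infection. Reviewing each control's record for empiric treatment makes little sense if untreated controls are to be left out. The analysis population is also commonly fixed in a statistical analysis plan, which is not at hand. Most of this stands: it makes shorthand for usual care the likelier reading and limits the weight of the point. It does not remove the conflict, because the one labelled null still describes a different comparison.

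A reader might infer that the sponsor intends to drop untreated controls, or that the trial's result will be biased. The protocol supports neither. No section plans such an exclusion, and the rejection rates above rest on assumed treated shares and error mixes.

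A reader might also say that undertreatment cannot occur at all in the literal comparator. That is too strong. F. Methods recognises PCR-positive patients whose antibiotics were not adequate, so a treated patient could still be undertreated.

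Finally, the null is directional. Rewriting it as equality of the two arms would bring in a two-sided null that the protocol does not state, so the correction should leave the direction alone.

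**Conclusion.** The point holds as a misworded hypothesis. The comparator in the only labelled null is not the randomised control group, and it largely leaves out one of the two errors that the endpoint counts. This conclusion needs no assumption beyond the protocol's own text. Any bias arises only if an analyst follows the phrase literally, and its size and direction cannot be determined from the document. The planned 43 per group, or 48 with dropout, is unaffected.

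A reader might further infer that the 21% control rate is wrong, since the protocol credits the same 2015 study with 21% inappropriate treatment and 86% overtreatment. That is not shown. These are different quantities, they may have different denominators, and the protocol gives neither denominator. Asking for them is an optional query and forms no part of this finding.

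**What to change.** Replace the null in A. Specific Aims with one sentence that keeps its direction: the proportion of patients appropriately treated for GC/CT, judged against PCR and counting both overtreatment and undertreatment as errors, is no greater among all patients randomised to RTAT plus PCR than among all patients randomised to PCR only.

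The cost is one sentence. Arms, data collection, sample size and trial conduct stay as they are.

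### Does the pooled GC/CT definition of inappropriate treatment let an infection left untreated count as appropriate treatment?

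*Protocol*

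**What the plan says.** The scoring rule is in the protocol, section B (Background Significance). For this study, treatment is inappropriate if it is "administration of antibiotics to treat GC/CT in the absence of GC/CT infection or failure to give antibiotics in the presence of GC/CT infection". The same paragraph makes PCR, not the rapid turnaround test (RTAT), the reference. Section E restates the primary outcome only in general terms, as the effect of the rapid test on treatment.

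Other places bear on the reading:

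- Section C (Research Design) lists four RTAT/PCR result combinations, each test being simply positive or negative. Its sample size paragraph describes the 21% control rate as the share of patients given wrong treatment.
- The exclusion criteria in section D name the organisms separately: "Patient who reports being treated for either gonorrhea or chlamydia in the preceding 3 months".
- Section F (Methods) says "A cervical swab sample will be analyzed with the RTAT" and "After results of the RTAT test are obtained the treating provider will be given the results". It also provides that a patient with a positive standard test is called back if "the subject did not receive adequate antibiotics will be contacted", which governs follow-up care and not outcome scoring.
- The Review of Literature says of current practice that "providers will tend to treat patients empirically for both STDs without any objective data".

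**The concern.** Both halves of the definition use the joint label GC/CT, and the second half says only that antibiotics were not given. Read as one pooled condition, any infected patient who receives any GC/CT treatment is scored as appropriately treated. That includes a patient with chlamydia treated only for gonorrhea, and a co-infected patient treated for one organism. In both, PCR has found an infection that the index visit left untreated.

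The protocol's introduction names undertreatment as one of the two harms behind the trial, so a primary outcome that cannot register some undertreatment deserves a check. The arms could also differ. Empiric treatment tends to cover both organisms, whereas a provider holding an RTAT result may treat only the organism reported. Any misclassification might then fall mainly on the RTAT arm and flatter it.

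**Working it through.** **1. What the two readings do.** There are three infected PCR states (GC only, CT only, both) and three treated states (for GC only, CT only, both), so 3 × 3 = 9 combinations.

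| PCR result | Treated for GC only | Treated for CT only | Treated for both |
|---|---|---|---|
| GC only | matches | infection untreated | extra treatment |
| CT only | infection untreated | matches | extra treatment |
| Both | CT untreated | GC untreated | matches |

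On the pooled reading all 9 score as appropriate: 3 match, 4 leave a PCR-positive organism untreated, and 2 treat an absent organism as well. Read organism by organism (antibiotics for GC without GC, or none for GC with GC; likewise for CT), the 4 score as inappropriate, and so do the 2. These are counts of logical possibilities, not shares of patients.

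**2. The plan's own sample size.** Inputs from section C: alpha 0.05, power 0.80, P0 = 0.21, P1 = 0, equal groups. Two-sided, with mean proportion 0.105:

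n = [1.960 × √(2 × 0.105 × 0.895) + 0.842 × √(0.21 × 0.79)]² / 0.21² = 32.2

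With continuity correction: (32.2 / 4) × [1 + √(1 + 4 / (32.2 × 0.21))]² = 41.2, so 42 per group against the stated 43. For 10% dropout, 43 / 0.9 = 47.8, giving the stated 48. The design figures reproduce closely, and the scoring question does not affect them.

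**3. The part that can be sized.** The RTAT runs on a cervical swab. Section C cites CT "sensitivities for endocervical, vaginal, and urine samples of 97.4%, 98.7%, and 97.6%, respectively", so the endocervical miss rate for CT is 1 − 0.974 = 0.026. The cited endocervical sensitivity for GC is 100.0%. A test error produces a disputed case when a co-infected patient has her CT missed and is then treated for GC only. The other test-error route, a missed CT with a false-positive GC, is negligible at the GC specificity of 99.9–100% in the Review of Literature.

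The protocol does not give the co-infection share c, so it is an assumption here. Expected RTAT-arm cases = n × c × 0.026, taking every missed CT as treated for GC only. Power is for Fisher's exact two-sided test at 0.05, with P0 = 0.21 and P1 = c × 0.026, adding cases to the RTAT arm alone.

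| Assumed c | P1 | Cases of 43 | Power, 43 per arm | Cases of 48 | Power, 48 per arm |
|---|---|---|---|---|---|
| 0 | 0 | 0 | 0.913 | 0 | 0.955 |
| 5% | 0.0013 | 0.056 | 0.901 | 0.062 | 0.947 |
| 10% | 0.0026 | 0.112 | 0.890 | 0.125 | 0.937 |
| 20% | 0.0052 | 0.224 | 0.868 | 0.250 | 0.918 |

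Only the unrealistic ceiling of universal co-infection (1.12 of 43) takes power below 80%, to 0.696.

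**4. The part that cannot be sized.** Single-organism treatment chosen by a provider, or given after an invalid or missing RTAT result, has no frequency in the protocol. As a pure assumption, suppose organism-level scoring added the same share of failures to both arms. The continuity-corrected requirement would go from 42 to 45, 47, 50 and 55 per group at 1%, 2%, 3% and 5%. Added to the RTAT arm alone, it would be 47, 54, 61 and 81. These are consequences of rescoring at invented rates and do not show that the present rule is underpowered.

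**The case for a change.** The best case for acting is that this is the only scoring rule shown for the primary outcome, and the protocol states it as the study definition instead of leaving it open. No other section requires treatment to match the organism found. A patient called back because her antibiotics were inadequate could, on the pooled reading, still count as appropriately treated. The trial is nonblinded, so a written rule helps those who review charts, and one sentence with one chart field would be cheap.

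Much of this stands. The text does not state organism matching, and the arms could in principle be affected differently. Three things weaken it.

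- Pooling is not established as the intention. Describing the planning rate as wrong treatment, and naming the two diseases separately elsewhere, fit organism-level scoring at least as well.
- How to score co-infection and partial treatment is detail that usually belongs in an analysis plan or coding manual. Neither that plan nor the data collection forms are shown.
- The obvious repair is contestable. Making undertreatment organism-specific while leaving overtreatment pooled means a single infection treated for both organisms never fails, while treatment directed by a test result can. The new failures would probably fall mainly on the RTAT arm. It might also part the endpoint from the 21% planning rate, whose scoring rule the protocol does not describe.

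**Conclusion.** The definition is ambiguous on this point but not shown to be wrong, and no change to the plan is called for. Analysts setting scoring rules would have to choose between pooled and organism-level scoring anyway, and can do so sensibly from the text, provided the choice applies to both halves of the definition alike.

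The derivable effect is 0.06 to 0.22 RTAT-arm patients of 43, with power at 87% or more. This rests on assumed co-infection of 5% to 20%, on the cited sensitivities holding against the site's PCR, and on every missed CT being treated for GC only. Provider-driven cases are unquantified. The stated tendency to treat empirically for both would put infected patients treated that way outside the four disputed combinations, and the protocol offers nothing from which to infer a material number in the RTAT arm. No effect on the trial's result has been shown.
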